2. The current study will be a randomized single-blinded placebo-controlled phase III clinical trial for this Investigational new device (SQ53 wipes) intended for the catheter cleaning in patients receiving home parenteral nutrition.
3. With ethanol lock therapy being phased out, there is no currently approved effective and readily available modality available in the United States to prevent CRBSI. On compassionate grounds it is imperative to use and to study SQ53 so that patients can benefit from this clinical trial.

Study design: Prospective randomized single-blinded placebo-controlled clinical trial

*Please note that the randomization will also be stratified by PICC/Tunneled catheter type.

Study objectives:

Primary objective:

1. To determine the effectiveness of SQ53 wipes in prevention of CRBSI in patients receiving home parenteral nutrition.

Secondary objectives:

1. To identify if there are any major or minor adverse effects such as skin irritation associated with the use of SQ53 wipes.

Inclusion criteria and patient recruitment:

1. Adult (age>18) patients requiring home parenteral nutrition support via PICC line or tunneled CVC.
2. Patients will be included via following process:
 - a. All patients managed by CCF HPN team, meeting the inclusion criteria will be sent a letter of information and full informed consent form.
 - i. Letter of information will be a cover letter informing patients about the clinical trial (letter attached)
 - ii. Informed consent form: Standard informed consent form with detailed information about the study as per the Cleveland Clinic guidelines.
 - iii. Letters will be sent in an alphabetical order for 10-15 patients each week to evenly distribute the work burden overtime.
 - b. Patients who are interested to enroll in the study will call our HPN team, and we will answer any questions that these patients might have.
 - i. The consent form will be again sent via email.
 - ii. HPN dietitian will take consent over the phone by using DocuSign and will document it in patient's chart in HPN database
 - iii. HPN dietitian will notify caring NST physician regarding patient's enrollment in the trial.

- c. HPN dietitian (or NST physician or both) will classify patient in either a High Risk, Low Risk or New Patient Category via specific criteria.
 - i. **Identification of high-risk patients** which will be determined by the following criteria:
 - 1. History of one or more CRBSI infection in the past 6 months

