 - 2. Immunocompromised state increasing the infection risk
 - a. Clinical determination based on comorbidities such as HIV, immunosuppressant medications, and steroids (prednisone >40mg per day)
 - 3. History of multiple catheter exchange in the past (greater or equal to 2 within the past 6 months) with difficult access
 - a. This determination to be made based on patient's history
 - ii. Identification of Low risk patients:
 - 1. Patients who do not meet High-risk criteria will be classified as Low risk patients
 - iii. New patients:
 - 1. New patients are the patients who are newly started on PN during their in-patient stay and those who have been on PN less than 6 months unless they had CRBSI in the time frame.
 - 2. These patients will receive information about the clinical trial by RNs who provide education as standard of care.
- d. Patients can also be enrolled in the study at the time of outpatient visit, or before discharge from the hospital.
- 3. Cleveland Clinic Home Infusion Pharmacy (CCHIP) will be informed about patient's enrollment and the risk category (High vs Low vs New patient) and the catheter type (PICC or tunneled)
 - a. CCHIP will perform stratified randomization and assign the patient to either Treatment (SQ53) or PLACEBO (Alcohol wipes) group.
- 4. Treatment group will also have the SQ53 impregnated wipe used on a remote site to check for hypersensitivity and any other skin reactions before it is deemed safe to use routinely in that patient.

5. All enrolled patient will need to agree to reach out to Home Nutrition Pager which is available 24x7 in case of noted adverse effect – this is standard of care for home PN patients.

Exclusion criteria:

1. Age less than 18 years
2. Women known to be pregnant (patient will be asked verbally- no pregnancy test will be performed)
3. Women of childbearing age who are planning a pregnancy
4. Women who are breastfeeding
5. Patient's refusal to enroll in the study at any point in time
6. Patients who refuse to use disinfectant wipes daily.
7. Patients who use port for their PN infusion.
8. Patients who are enrolled in other clinical trials with investigational drugs or device

Blinding and Randomization:

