- **Blinding:** This will be a single blinded study and the NST-providers will be blinded to the treatment arm that the patient is assigned to. A clinician will initially interview the patient and at the time of enrollment into the clinical trial, obtain an informed consent after which the patient will be enrolled in the study.
- **Blinding the patients is not possible** due to several reasons:
 - o SQ53 and alcohol wipes will have labels on them
 - o differences in physical characteristics (smell) which are distinct for alcohol wipes and SQ53
 - o therefore, it is unfeasible to blind patients to the intervention.
- **However,** despite being an unblinded study, outcome of our study is not likely to be affected as the primary outcome measure is diagnosis of CRBSI which is based on the Positive Blood Culture and is not very likely to be impacted by a placebo effect.
- **Randomization with a placebo:** Once patients are enrolled into our study, patient's information will be discussed with the pharmacy who will assign the patient to either a treatment or a placebo group.

- Patients will be randomized in 1:1 ratio to receive either SQ53 or placebo. The randomization process will be stratified randomization, followed by blocked randomization in each stratum. Stratification will be done on two factors: CRBSI risk category and catheter type. CRBSI risk categories will be determined by the clinicians or NST staffs 1. High risk (1 or more CRBSI in previous 6 months) 2. Low risk (no CRBSI in previous 6 months) 3. New patient. Catheter types will be 1. Tunneled central catheters 2. Non-tunneled central catheters. The design has $3 \times 2 = 6$ strata. Blocked randomization will subsequently done in order to avoid serious imbalance in the number of participants assigned to treatment or placebo group. The block sizes will be determined by Cleveland Clinic Home Infusion Pharmacy.

Intervention:

Patients who qualify to enroll in the trial and sign an informed consent will be enrolled and will be eligible to receive either the intervention or the placebo. Providers will be blinded to which group patient is assigned to.

- Pharmacy (Cleveland Clinic Home Infusion Pharmacy will perform randomization and will assign patients to the groups)
- **All patients in the study will receive the wipes (Treatment group = SQ53 wipes, Placebo = alcohol wipes)**
 - o Provide packs of sterile wipes to the patient for daily use (**external use only**)

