 - o Wipes should be used daily, as well as, when the dressing is changed, by wiping the catheter surface and hubs for at least 15 seconds
 - o **Daily use:** Patients will be given instruction to clean the exterior and the caps of the intravenous catheters by following a sterile technique. This should be done before and after each use (i.e. PN infusion)
 - o **At the time of dressing change:** Standard practice is to change the dressing every week. At this time the patient will use wipes to clean the catheter exit site and skin around the catheter exit site, catheter exterior and catheter caps prior to applying the new dressing
 - o Wipes will be provided to the patient free of cost (material will be sponsored by the JVS company)

- Patients in both the groups will continue to use the standard care: i.e. ethanol (curos) caps, saline locks.

Data collection:

1. A registry of enrolled patients will be prepared. CCF HPN service has an approved database of patients receiving home parenteral nutrition. There are no additional HPI that will be collected as a part of enrollment in the study. The patient data is already collected into a password protected HPN database as current standard of practice. This data is routinely collected and updated by HPN dietitians.

Sample data sheet of primary objectives (data in *italics blue font* is for example):

Patient Nomenclature:				
SQ53/Treatment Group: Patient T1, Patient T2....				
Placebo Group: Patient C1, Patient C2....				
	Pre vs Post SQ53 trial enrollment	Number of Confirmed CRBSI in 6 months	Number of total admissions for CRBSI in 6 months	Number of catheters changed due to CRBSI in 6 months
Patient T1	Pre	2	3	0
	Post	0	1	0
Patient T2	Pre			
	Post			
Patient C1	Pre	0	1	0
	Post	1	1	1

Patient C2	Pre			
	Post			
Patient C3	Pre			
	Post			

Data protection, processing and, analysis of the data:

1. CCF HPN service has an approved database of patients receiving home parenteral nutrition. The patient data is already collected into a password protected HPN database as current standard of practice. We will use REDCap for data entry for analysis. All data will be password protected.
2. We plan to perform both "**Per Protocol**" and "**Intention to treat analysis**".

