3. Patients whose compliance is less than 90 percent will be excluded from Per Protocol analysis; however, those patients will be accounted in intention to treat analysis. Patients who developed skin reaction in remote site (e.g., forearm) will be excluded from Per Protocol analysis, but will be included in intention to treat analysis
 - a. Compliance will be determined by HPN dietitian at the time of phone/virtual visit encounters: patient will be asked about their disinfectant wipe use and compliance.
4. Our primary outcome measure (as listed in above data sheet) will be differences in the CRBSI rate at 6 months after patient enrollments into the trial (i.e. SQ53 use). We will also perform sub-analysis by utilizing patients as their own controls. Please see the detailed timeline below.
5. We will also analyze the differences in the number of admissions for CRBSI (which would include admission with suspect CRBSI), as well as, overall number of catheters changed for confirmed and suspected CRBSI.
6. We will perform Poisson Regression analysis to compare the rates and 95 % confidence interval of the differences in CRBSI rates and CRBSI admissions.
7. We will also perform a descriptive analysis identifying the most common microorganisms causing the CRBSI in the periods both before and during the SQ53 therapy.
8. We will also perform a survival analysis to plot a Kaplan-Meier curve

9. We will collect mortality data of patients. We will report an overall mortality, as well as, CRBSI-specific mortality in patients using SQ53 for CRBSI prevention.

Sample size and power calculation:

1. In the un-published study conducted in India SQ53 has been reported to reduce the CRBSI rate by 94%. We expect this effect size to be lower in our cohort. We performed our sample size calculation by utilizing the data reported in our previous study which reported CRBSI rates in high risk PN patients (Pre-ELT CRBSI rate= 3.53 and post-ELT 1.65 per 1,000 catheter days). Considering current CRBSI rate in our high-risk population to be 1.65 per 1000 catheter days, we will need a sample size of 46 patients to identify a 50% reduction in CRBSI rate with alpha of 0.05 and 80 % power.

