Nov 2020 – Dec 2020	
 1. Once IRB is approved: send letters to patients 2. Obtain informed consent and enroll patients 3. Risk category assessment 4. Baseline data collection 5. Randomization 6. Shipment of SQ53 or Placebo supply 
Personnel responsibility:
 
 1. Sending letters to patients: 
 - Letter has been drafted and ready, to be printed and mailed to the patients by study coordinator

	
2. Obtain informed consent
 
 - HPN dietitian 
3. Risk category assessment
 
 - HPN dietitian & NST staff 
4. Baseline data collection
 
 - HPN team, Nutrition Fellows, Study coordinator 
5. Randomization
 
 - DDSI statistician / CC Home infusion Pharmacy 
6. Supplying SQ53 and placebo wipes
 
 - CC Home infusion pharmacy
Dec 2020 to June 2021	
1. Continuation and monitoring phase of the study
 
2. Answer patient's concerns and collect data regarding specific side effects (if any)
 
3. Continue standard routine follow up: i.e. with labs, or during phone encounters
 
Personnel responsibility:
 
 - HPN dietitian, NST staff and Nutrition fellows
June 2021	
1. Perform interim analysis of the data
 
Personnel responsibility:
 
 - DDSI statistician
July 2021 to Dec 2021	
1. Continue the study for another 6 months and continue to enroll the patients
 
Personnel responsibility:
 
 - HPN dietitian, NST staff and Nutrition fellows
Jan 2022	
1. Final Analysis of the data
 
2. Reporting of the study findings
 
Personnel responsibility:
 
 - Statistical analysis: DDSI statistician

	- Reporting: All investigators
--	--------------------------------

References:

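### Collection of adverse effects, the only secondary objective, is neither standardised nor the same in both arms, so a clean SQ53 result in about 30 patients would be weak evidence

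*Combined protocol and SAP*

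**What the plan says.** The single item under Secondary objectives is "To identify if there are any major or minor adverse effects such as skin irritation associated with the use of SQ53 wipes". Several places bear on how such effects would come to be recorded.

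- **Patient reports.** Inclusion criteria and patient recruitment, item 5: "All enrolled patient will need to agree to reach out to Home Nutrition Pager which is available 24x7 in case of noted adverse effect".
- **Skin test.** Item 4 of the same section: "Treatment group will also have the SQ53 impregnated wipe used on a remote site to check for hypersensitivity and any other skin reactions". This takes place before routine use. No counterpart is given for the alcohol-wipe arm.
- **Staff collection.** The Timeline row for the monitoring phase lists "Answer patient's concerns and collect data regarding specific side effects (if any" and assigns it to the dietitian, NST staff and fellows, alongside routine follow-up by labs or phone. It gives no interval or content.
- **Dietitian encounters.** Data protection, processing and, analysis of the data, item 3a, says how compliance is judged: at phone or virtual encounters the "patient will be asked about their disinfectant wipe use and compliance".
- **Data fields.** Data collection, item 1, relies on the existing home PN database and says "There are no additional HPI that will be collected as a part of enrollment in the study". REDCap is planned for data entry. The one sample sheet shown is labelled for the primary objectives and has no adverse-effect column.
- **Analysis.** Items 4 to 9 of the analysis section cover CRBSI, admissions, catheter changes, organisms, a Kaplan-Meier curve and mortality. None summarises skin or other adverse effects.

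On blinding, Blinding and Randomization says of patients "therefore, it is unfeasible to blind patients to the intervention", while under Intervention "Providers will be blinded to which group patient is assigned to".

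**The concern.** A minor reaction is recorded only if someone asks about it or the patient volunteers it. The plan intends to collect side effects, but does not say what is asked, how often, of whom, or where the answer goes. What it does specify depends on the arm: SQ53 patients get a skin test and alcohol-wipe patients do not, and all patients know which wipe they have. The protocol defends unblinded patients on the ground that the primary outcome rests on a positive blood culture. That defence does not carry over to self-reported irritation.

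Two things are at stake. A report of no reactions on SQ53 would appear to confirm the statement under Safety concerns that the product does not irritate skin, when it might partly reflect reactions nobody recorded. And any comparison with alcohol wipes would mix a difference between the wipes with a difference in how hard reactions were looked for.

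**Working it through.** The plan states no adverse-effect rate, safety sample size or safety power, so it has no figure of its own to reproduce. The check has two parts.

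**1. What each route delivers**

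- Pager: both arms, started by the patient, no severity threshold, patient unblinded.
- Remote-site test: SQ53 arm only, before routine use. It cannot show irritation that develops over the 6 months of use, which includes cleaning the exit-site skin at each weekly dressing change.
- Side-effect collection in the Timeline: not restricted by arm, but no question, interval, grading or data field.
- Item 3a encounters: content stated only for compliance.
- Analysis items 4 to 9: no adverse-effect summary by arm.

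No route is both standardised and identical in the two arms.

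**2. What a clean result would show**

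Input from the plan: 30 patients per arm (Sample size and power calculation, item 2; 46 × 1.3 = 59.8, or 60 in two groups). Assumptions: the true reaction rate *p* and the share of reactions captured *s*.

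Upper two-sided 95% limit after 0 of 30 with full capture: 1 − 0.025^(1/30) = 11.6%.

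With capture *s* the recorded rate is *p* × *s*, so the limit on the true rate is 11.57%/*s*: 15.4% at 75%, 23.1% at 50% and 46.3% at 25%.

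Chance of recording no reaction in 30 patients: (1 − *p* × *s*)^30.

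| True rate (assumed) | Capture 100% | 75% | 50% | 25% |
|---|---|---|---|---|
| 5% | 21.5% | 31.8% | 46.8% | 68.6% |
| 10% | 4.2% | 9.6% | 21.5% | 46.8% |
| 20% | 0.1% | 0.8% | 4.2% | 21.5% |

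For example, at 10% and half capture: (1 − 0.10 × 0.50)^30 = 0.95^30 = 21.5%.

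Unequal capture works in either direction. Take a true rate of 10% in both arms, or 30 × 0.10 = 3 expected reactions each. With 75% capture on SQ53 and 50% on alcohol wipes, 2.25 against 1.5 are expected to be recorded. With the capture shares swapped, it is 1.5 against 2.25. The wipes do not differ in either case.

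**The case against.** The strongest reply is that side-effect collection is planned. The Timeline says so and names who does it, next to the phone encounters. Item 3a exists to define compliance for the per-protocol set. A reader might infer from it that the calls ask about wipe use and nothing else, or that they follow a fixed schedule; the text says neither. The statement that nothing additional is collected concerns enrolment and cannot exclude all further trial data, since compliance and side effects are to be collected. The sample sheet is for the primary objectives, so a missing adverse-effect column there proves little. All of this stands, and it rules out any claim that the plan will not ask.

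A reader might also suppose that patients page only for alarming events, or that the bias must favour a clean SQ53 result. The documents support neither. The pager rule has no severity threshold, and patients using a new wipe after a skin test might over-report. The SQ53-only test could itself raise the SQ53 count.

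The capture shares and true rates above are assumptions, and small numbers alone can give a clean result: at a true rate of 5%, full capture still yields none in 21.5% of trials. Finally, the objective is descriptive, and a between-arm interval goes somewhat beyond it. That is fair, but in a randomised trial the comparison arm is what separates the effect of SQ53 from background irritation.

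What the reply does not supply is a common question, an interval, a data field or a summary by arm.

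**Conclusion.** The point stands in a limited form. Side-effect collection is mentioned but not standardised, the specified parts differ by arm, and no adverse-effect field or between-arm summary is given. Recorded reactions could be too few or unequal, with the direction of bias uncertain.

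The size is clear on one side only. That 0 of 30 excludes no rate below 11.6% follows from the planned arm size and needs no assumption about under-reporting beyond full capture. The rise in the chance of a clean result from 4.2% to between 9.6% and 46.8% rests on an assumed true rate of 10% and capture of 75% down to 25%; nothing in the documents fixes either. This is a worthwhile, inexpensive improvement to the secondary objective. It does not touch the primary analysis and does not show that SQ53 irritates skin.

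One related matter affects the denominator. Safety concerns, item 3, removes patients with a hypersensitivity skin reaction from the study, whereas analysis item 3 keeps those who react at the remote site in the intention-to-treat analysis. These may be meant to be compatible, but the text does not say how, and the passages must be reconciled.

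**What to change.** - **Ask.** At the dietitian phone or virtual encounters in item 3a, put the same fixed question to every patient in both arms: any skin or exit-site irritation, or any other reaction, since the last contact (yes/no, site, severity, wipe stopped yes/no). State the intended interval between contacts.
- **Record.** Enter the answers in REDCap, and record them so that they do not reveal the arm to the blinded NST providers.
- **Report.** Give the proportion with at least one solicited reaction by randomised arm, among all randomised patients, with the difference and 95% CI. List remote-site test reactions and pager reports separately, because the first exists in one arm only and the second is unsolicited.
- **Reconcile.** Make Safety concerns, item 3, and analysis item 3 agree on the status of patients who react, so that the safety denominator is unambiguous.

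The cost is one scripted question at encounters already planned and a few REDCap fields, with no extra visits or staff. The downside is that asking will raise the reported reaction rate in both arms, and the report should say so.

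### The 6-month outcome window opens at enrolment, which the plan equates with SQ53 use, although randomisation, shipment and an SQ53-only skin check come later

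*Combined protocol and SAP*

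**What the plan says.** All references are to the combined protocol and SAP.

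- **Outcome window.** Item 4 of the data protection, processing and analysis section defines the primary outcome as "differences in the CRBSI rate at 6 months after patient enrollments into the trial (i.e. SQ53 use". The sample data sheet under Data collection divides each patient's counts by "Pre vs Post SQ53 trial enrollment".
- **Randomisation follows enrolment.** Under Blinding and Randomization: "Once patients are enrolled into our study, patient's information will be discussed with the pharmacy who will assign the patient" to an arm.
- **Shipment follows randomisation.** The Timeline row for Nov–Dec 2020 lists consent and enrolment, risk category, baseline data, randomisation and, last, "Shipment of SQ53 or Placebo supply".
- **A skin check in one arm only.** Item 4 of Inclusion criteria and patient recruitment says "Treatment group will also have the SQ53 impregnated wipe used on a remote site to check for hypersensitivity" and other skin reactions "before it is deemed safe to use routinely in that patient". No duration is given.
- **Enrolment in hospital.** Item 2d of the same section allows enrolment before discharge.
- **Per-protocol set.** Item 3 of the analysis section removes patients with compliance under 90%, and "Patients who developed skin reaction in remote site (e.g., forearm) will be excluded from Per Protocol analysis". It removes patients, not time before first use.

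No section defines a patient-level day 0 other than enrolment, asks for the date of first wipe use, limits the gap, or says how infections before first use are counted. Item 7 describes organisms before and during SQ53 therapy, which is a different boundary. The Kaplan-Meier curve in item 8 has no stated time origin.

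**The concern.** Enrolment and use are treated as one date, but the plan's own steps separate them. The interval has two parts with different consequences.

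1. **Enrolment to randomisation.** No arm exists yet, so an infection here cannot be an effect of either wipe. Counting it adds events and time that are alike in both arms in expectation, which dilutes the contrast.
2. **Randomisation to first routine use.** This covers shipment, any remaining hospital stay and, in the SQ53 arm, the skin check. It belongs in an intention-to-treat comparison. It does not belong in an analysis meant to describe use: the per-protocol analysis, or the sub-analysis with patients as their own controls, whose Pre/Post boundary is misplaced by the whole lag.

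The stake is attribution. With few expected infections per arm, the analysis should be able to say whether each one fell before randomisation, before use or during use. The dates that the plan describes do not allow this.

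**Working it through.** **Inputs from the plan.** Control rate 1.65 per 1,000 catheter days and a 50% reduction, so 0.825 per 1,000 (Sample size, item 1); 30 patients per group (item 2); a 6-month window, taken as 365/2 = 182.5 days.

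**Assumptions.** The lag L from enrolment to routine use is not in the plan; 7, 14 and 28 days are used as a range. The rate is constant, and SQ53 patients not yet using the wipe have the control rate.

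**Step 1: does the plan's sample size allow for a lag?** Its figure of 46 can be reproduced as a comparison of two Poisson rates with one-sided alpha 0.05 and 1,000 catheter days per patient:

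n per arm = (1.645 + 0.842)² × (1.65 + 0.825) / (1.65 − 0.825)² = 22.5, rounded up to 23, or 46 in total.

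The full 50% reduction applies to all counted time, so nothing is allowed for a lag. (The mismatch between 1,000 days and a 6-month window is a separate matter.)

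**Step 2: observed ratio if the whole lag is counted.**

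Observed ratio = [L + 0.5 × (182.5 − L)] / 182.5

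| L (days) | Calculation | Observed ratio | Observed reduction |
|---|---|---|---|
| 0 | 91.25/182.5 | 0.500 | 50.0% |
| 7 | 94.75/182.5 | 0.519 | 48.1% |
| 14 | 98.25/182.5 | 0.538 | 46.2% |
| 28 | 105.25/182.5 | 0.577 | 42.3% |

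**Step 3: events.** Expected control infections are 30 × 0.00165 × 182.5 = 9.0; expected SQ53 infections with no lag are 4.5. In a 14-day lag the SQ53 arm would expect 30 × 0.00165 × 14 = 0.69 infections. Half of these would have occurred under SQ53 anyway, so the net excess is 0.35. For 7 and 28 days the net excess is 0.17 and 0.69.

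**Step 4: against sampling error.** The standard error of the log rate ratio is about √(1/9.0 + 1/4.5) = 0.58. The shift in the log ratio is ln(0.519/0.5) = 0.04 at 7 days, ln(0.538/0.5) = 0.07 at 14 and ln(0.577/0.5) = 0.14 at 28.

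**Step 5: what each change of day 0 recovers.** Write L = G + S, with G from enrolment to randomisation and S from randomisation to routine use. Starting at randomisation replaces L by S in the formula. If L = 14 with G = S = 7, the intention-to-treat ratio moves from 0.538 to 0.519, not to 0.500. If G is zero, it does not move. Starting at first use removes all of L, but only in the analyses where that start is appropriate.

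**The case against.** **The wording may be loose.** The parenthesis in item 4 could simply mean the period after joining the trial. Item 4 also points to the Timeline, which puts consent through shipment in a start-up step and then shows a monitoring phase of about six months. But the Timeline is a project calendar and sets no clock for a patient. The data sheet names enrolment as the divide, so enrolment is the rule as written.

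**The effect is small, and its size is assumed.** This stands. No lag is stated, the skin check could be very short, and the plan does not say how long before discharge a patient may enrol. The shift is toward no difference and well inside the sampling error.

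**Stronger readings.** A reader might infer that the plan systematically loads infections onto SQ53. The documents do not support that: only the skin check is specific to one arm, its length is not given, and both arms keep the standard caps and saline locks throughout. A reader might also take 0.52 to 0.58 as the bias that an intention-to-treat correction would remove, or conclude that intention-to-treat should start at first use. Neither follows. Delay after randomisation is properly counted in intention-to-treat, and removing it would condition on a step that differs by arm.

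**The compliance rule may already catch long lags.** A patient with 28 of 182.5 days unused has about 85% compliance and would leave the per-protocol set, if compliance is measured over the whole window. The denominator is not stated, so this cannot be relied on. Under the same reading, lags up to about 18 days (10% of 182.5) could pass.

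**Conclusion.** The point holds as a defect in the definition of day 0, with a probably small effect. The stated rule counts infections before randomisation as outcomes, and puts time without wipes into the two analyses meant to reflect use.

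The quantified range applies to the whole lag and rests on assumed lags, a constant rate, a true ratio of 0.50 and a pre-use rate equal to the control rate. Intention-to-treat can recover only the pre-randomisation share, which the documents do not let one estimate. The per-protocol and own-control analyses are affected more directly, because the whole lag is misplaced in them.

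The documents do not show that any infection will fall in the interval, that the randomised comparison is invalid, or that the bias against SQ53 is material. The change is worth making because it costs little, and the events cannot be reliably reassigned later if the dates were not recorded.

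**What to change.** In item 4 of the analysis section and in the data sheet:

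1. **Intention-to-treat and Kaplan-Meier.** Define day 0 as the randomisation date in both arms. Count events and catheter days for 6 months from it, and keep delay after randomisation in. Assign infections before randomisation to 'Pre'.
2. **First routine use.** Record this date the same way in both arms; dietitians already ask about wipe use at phone or virtual visits. Patients with no such date stay in intention-to-treat.
3. **Per-protocol and own-control analyses.** Start the per-protocol window, and set the Pre/Post boundary of the own-control sub-analysis, at first routine use. Because that boundary differs from the one in step 1, derive the two sets of counts separately from dated events.
4. **Interpretation.** State that the per-protocol analysis from first use is supportive, since first use comes after randomisation and its timing can differ by arm.

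**Cost.** Some protocol wording and one new date field (the pharmacy that assigns patients should already hold the randomisation date). Follow-up ends slightly later for some patients. The first-use start drops events between randomisation and use over an interval that may be longer in the SQ53 arm, which is why it should not carry the primary conclusion.
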